7.5 Study size

The main objectives of the ARIADNE study are to describe:

- 1. The profiles of patients who are prescribed sacubitril/valsartan or SoC in terms of demographics, medical history, HF status, comorbidity burden.
- 2. The profiles of patients who are prescribed sacubitril/valsartan and do not achieve and maintain the target dose of 200 mg BID within the observation period of 12 months in terms of demographics, medical history, HF status, comorbidity burden.

Overall the present NIS will enroll 6000 patients on SoC and 6000 patients on sacubitril/valsartan. Accordingly, 6000 patients will be available in each group for the first main objective.

In the randomized controlled study TITRATION (Senni 2015), 76.2% of patients were able to reach and maintain the target dose of sacubitril/valsartan over 12 weeks, while 23.8% of patients were not. Despite the absence of other data on the titration of sacubitril/valsartan in the literature, in real-life a higher proportion of patients failing up-titration to the target dose can be expected, due to tolerability reasons and lack of patients' or physicians' compliance. Assuming that the actual lack of up-titration could realistically be as high as 50% of all patients, 3000 sacubitril/valsartan patients will be available for the second of the two main objectives.

The two main objectives are focused on description of patient profiles. With respect to the first main objective, a total of 6000 patients in each group will allow to estimate patient profile parameters with the following precision: The two-sided 95% confidence interval (CI) for qualitative parameters (e.g. gender) will be no longer than 2.6% (i.e. estimate \pm 1.3%), and 95% CIs for quantitative parameters (e.g. age) will not exceed 5.0% of the underlying standard deviation (SD) (i.e. estimate \pm 0.025*SD).

The number of SoC patients enrolled in phase 1 and in phase 3 respectively (first objective) and the number of patients on sacubitril/valsartan not achieving the target dose (second objective) are expected to be approximately 3000 each. With a sample size of 3000 patients, the two-sided 95% CI for qualitative parameters (e.g. gender) will be no longer than 3.6% (i.e. estimate \pm 1.8%), and 95% CIs for quantitative parameters will not exceed 7.2% of the underlying standard deviation (SD) (i.e. estimate \pm 0.036*SD).

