7.2 Setting

7.2.1 Population

The present study will include consecutive HFrEF patients treated by office-based cardiologists or selected primary care physicians (recognized as HF specialists) across Europe.

The study will include overall 6000 patients on SoC and 6000 patients on sacubitril/valsartan.

Considering that the different local regulations on patient management and reimbursement can significantly impact clinical practice, patient numbers will be allocated to bigger countries and/or clusters of smaller countries with similar healthcare systems in order to ensure the representativeness of the sample.

Enrollment will start in each country when sacubitril/valsartan is available for clinical use. Assuming that the penetration of sacubitril/valsartan into clinical practice will be slow immediately after launch, the enrollment of sacubitril/valsartan patients will take a significantly longer time than including SoC patients. At each country level the enrollment of sacubitril/valsartan patients will be continuous, while the enrollment of SoC patients will be divided into two phases, where approximately one half is immediately enrolled at the start of the study and the other half is enrolled during the last part of enrollment into the sacubitril/valsartan group (see Figure 7-1). By structuring the enrollment of SoC patients in this two-wave pattern, the possibility is created to compare the baseline demographic and medical characteristics of patients that drive the choice of physicians toward individualized SoC or sacubitril/valsartan (main objective) and see if their approach changes over time, after the launch of sacubitril/valsartan.

LCZ696 launch in Country A ~ 50 % ~ 50 % SoC SoC 100% LCZ696 Phase 2 Phase 1 Phase 3 12 months В ~ 50 % ~ 50 % LCZ696 launch in Country SoC SoC 100% LCZ696 Phase 1 Phase 2 Phase 3 12 months S ~50 % ~ 50 % LCZ696 launch in Country SoC 100% LCZ696 Phase 1 Phase 2 Phase 3

Figure 7-1 Enrollment schedules (examples) on single country level

Overall enrollment: 24 months

Enrollment schedule for each country will depend on enrollment numbers in SoC and sacubitril/valsartan groups and thus might need to be divided into phases, where SoC enrollment is split up in two phases, while LCZ696 enrollment is continuous (examples A-C). SoC = standard of care, LCZ696 = sacubitril/valsartan

12 months

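### The CI widths in Section 7.5 are written as firm maxima but hold only if patients are independent, which recruitment within practices does not guarantee

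*Protocol*

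**What the plan says.** Protocol Section 7.5 (Study size) justifies the study size by precision. For the first main objective, "a total of 6000 patients in each group will allow to estimate patient profile parameters with the following precision": the 95% "confidence interval (CI) for qualitative parameters (e.g. gender) will be no longer than 2.6"% (printed as ±1.3%), and "95% CIs for quantitative parameters (e.g. age) will not exceed 5.0% of the underlying standard deviation (SD"), printed as ±0.025 SD.

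For the SoC patients of each enrolment phase, and for sacubitril/valsartan patients who do not achieve the target dose, about 3000 are expected. "With a sample size of 3000 patients, the two-sided 95% CI for qualitative parameters (e.g. gender) will be no longer than 3.6"% (±1.8%), and "95% CIs for quantitative parameters will not exceed 7.2% of the underlying standard deviation (SD"), printed as ±0.036 SD.

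Section 7.5 does not say that patients are taken as independent. It gives no design effect, ICC, number of sites or patients per site.

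On recruitment, Section 7.2.1 says: "The present study will include consecutive HFrEF patients treated by office-based cardiologists or selected primary care physicians (recognized as HF specialists) across Europe". On countries it says that "patient numbers will be allocated to bigger countries and/or clusters of smaller countries with similar healthcare systems".

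Section 7.7 plans descriptive analyses with confidence intervals and no testing, and leaves the statistical procedures to a separate SAP. Section 7.9 (limitations) does not mention clustering.

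**The concern.** The widths are worded as guarantees. A guarantee of this kind rests on the variance formula behind it, and that formula treats each patient as a separate draw from the population. Here the patient reaches the study through a physician, and each physician contributes a run of consecutive patients.

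The protocol itself expects care to differ by place and provider. The rationale in the Abstract names urban or rural setting, distance to specialised centres and local budgets. Section 7.5 attributes part of the expected failure to reach the target dose to physicians' compliance. Patients of one practice may therefore resemble each other more than patients of different practices.

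Confidence intervals are the only inferential output of this study. If within-site correlation is appreciable, one of two things happens for proportions near 50%. Intervals that allow for it exceed the promised width, or intervals that ignore it keep the width and cover less than 95%. In either case, the precision statement behind the study size is too favourable.

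**Working it through.** **Inputs from the protocol (Section 7.5):** n = 6000 and n = 3000; two-sided 95%; ceilings of 2.6% and 5.0% of SD (n=6000), and 3.6% and 7.2% of SD (n=3000).

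**Inputs not in the protocol (assumptions):** m = 5 to 20 patients per site per group; ICC 0.01 to 0.05; sites of equal size.

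**Step 1: reproduce the stated widths under independence.** Proportion at p = 0.5: length = 2 × 1.96 × √(0.25/n). Mean: length = 2 × 1.96 × SD/√n.

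| n | Proportion | Stated | Mean, % of SD | Stated |
|---|---|---|---|---|
| 6000 | 2.53% | 2.6% | 5.06% | 5.0% |
| 3000 | 3.58% | 3.6% | 7.16% | 7.2% |

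Exact (Clopper-Pearson) lengths for the proportions are 2.55% and 3.61%, so the choice of interval hardly matters. The stated figures are the independent-patient formula, with a design effect of 1. The one departure is 5.0% of SD: the half-width is 0.0253 SD, printed as 0.025 and doubled. A true ceiling of 5.0% would need (2 × 1.96/0.05)² ≈ 6147 patients.

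**Step 2: how much clustering each ceiling tolerates.** Length grows with √DEFF, so the limit is (stated/computed)².

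- 2.6% at n=6000: (2.6/2.530)² = 1.056
- 3.6% at n=3000: (3.6/3.578)² = 1.012
- 7.2% of SD at n=3000: (7.2/7.157)² = 1.012
- 5.0% of SD at n=6000: (5.0/5.061)² = 0.976, so no slack at all

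With DEFF = 1 + (m − 1) × ICC, the 2.6% ceiling fails at p = 0.5 once ICC exceeds 0.056/(m − 1): 0.014 for 5 per site, 0.006 for 10 and 0.003 for 20.

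**Step 3: size under assumed values, n=6000, p = 0.5.** Coverage of a simple CI = 2Φ(1.96/√DEFF) − 1.

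| m per site | ICC | DEFF | Effective n | Length | Coverage of simple CI |
|---|---|---|---|---|---|
| 5 | 0.01 | 1.04 | 5769 | 2.58% | 94.5% |
| 10 | 0.05 | 1.45 | 4138 | 3.05% | about 90% |
| 20 | 0.05 | 1.95 | 3077 | 3.53% | about 84% |

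The first row still meets the ceiling.

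**Step 4: n=3000.** If the 3000 come from the same sites (a further assumption), m is about half as large. With ICC 0.05, m = 5 gives DEFF 1.20 and a length of 3.92%; m = 10 gives DEFF 1.45 and 4.31%. The stated ceiling is 3.6%.

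**Step 5: proportions away from 50%.** The length also scales with √(p(1 − p)). At DEFF 1.45 and n=6000, the 2.6% ceiling still holds for p up to about 0.24, and by symmetry for p from about 0.76.

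**The case against.** The strongest reply has five parts.

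- **No shortfall is demonstrated.** A reader might infer that the promised precision is not met. The documents do not support that: they give no ICC or site size, some plausible values keep the 2.6% ceiling, and the break points apply at p = 0.5. This stands. The point is that the ceilings are not guaranteed and have little room, not that they are known to fail.
- **Countries are not clusters.** A reader might count countries as a second level of clustering and obtain far larger inflation. Section 7.2.1 allocates patient numbers to countries or groups of countries, so country is a fixed stratum. It may raise a weighting question, but it does not inflate the variance in this way. This stands; the relevant unit is the site.
- **No simple CI is prescribed.** Section 7.7 leaves procedures to the SAP. This stands, so the coverage figures are conditional on intervals that ignore site. It does not rescue Section 7.5, where the widths are already fixed.
- **The arithmetic is right.** This is true for independent data, apart from the 5.0% rounding slip, which has no practical consequence by itself. The fault is an unstated assumption behind a firm promise.
- **Section 7.5 covers patient profile items such as age and gender, where site correlation may be small.** This is fair, and it limits the likely size. But profile also includes HF status, medical history and comorbidity, and the n=3000 ceilings tolerate an ICC of only about 0.003 even with 5 patients per site (0.012/4).

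**Conclusion.** The concern holds in a limited form. The Section 7.5 widths are what the study would achieve with independent patients. They are presented as maxima, while the design recruits within practices. At p = 0.5 they tolerate design effects of only about 1.06 (2.6%) and 1.01 (n=3000). The 5.0% of SD figure is already 5.06% under independence.

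How far actual intervals would exceed the ceilings cannot be determined from the protocol. Under the assumed range for n=6000, the length at p = 0.5 runs from 2.58%, within the ceiling, to about 3.53%. Proportions far from 50% may stay within it throughout. No main objective is invalidated and the case for enrolling 6000 per group is not overturned; what needs correcting is the stated precision.

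**What to change.** In Section 7.5:

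1. Replace the wording that sets maxima with widths stated to assume independent patients.
2. Add widths over a stated range of design effects, computed from the planned patients per site and a range of ICC. Do this separately for n=6000 and n=3000, since a subgroup has fewer patients per site.
3. Correct 5.0% to 5.1% of SD.
4. State that reported CIs use a variance robust to clustering by site, with country as a fixed stratum. The technical detail can stay in the SAP.

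The cost is a few sentences and a standard analysis procedure. The stated precision becomes less favourable and the reported intervals wider. Enrolment does not change.

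### Section 7.5: with 6000 patients per group the 95% CI for a mean is 5.06% of the SD wide, so the stated upper bound of 5.0% is narrowly missed

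*Protocol*

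**What the plan says.** Protocol Section 7.5 (Study size) first fixes the numbers: "6000 patients will be available in each group for the first main objective". It then reports the precision that this size gives for patient-profile parameters, as two-sided 95% confidence intervals:

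- Qualitative parameters, n = 6000: full width at most 2.6% (± 1.3%).
- Quantitative parameters, n = 6000: the interval "will not exceed 5.0% of the underlying standard deviation", with the half-width given as ± 0.025 SD.

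The same two statements follow for n = 3000, the approximate size expected for each wave of standard-of-care enrolment and for the sacubitril/valsartan patients who do not achieve the target dose:

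- Qualitative parameters, n = 3000: full width at most 3.6% (± 1.8%).
- Quantitative parameters, n = 3000: full width at most 7.2% of the SD (± 0.036 SD).

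All four are worded as upper limits, not as approximate values.

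**The concern.** A figure offered as a limit has to lie at or above the true value. For a mean with n = 6000 the true width lies slightly above the limit given.

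The two pairs of figures also hint at this without any recalculation. A proportion at its worst case (p = 0.5) has an SD of 0.5. At the same n, the interval for a mean in SD units is therefore exactly twice as wide as the worst-case interval for a proportion. The n = 3000 pair keeps that relation (3.6% and 7.2%). The n = 6000 pair does not (2.6% and 5.0%).

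Section 7.7 plans descriptive analysis with confidence intervals and no hypothesis tests, so these precision statements are the section's only quantitative account of what the study size delivers. What is at stake is the accuracy of one of them, for the first main objective.

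**Working it through.** **Inputs, all from Section 7.5**

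- Confidence level: 95%, two-sided, so z = 1.95996.
- Group size for the first main objective: n = 6000.
- Size of the smaller sets, used to check the formula: n = 3000.
- Stated limits on full width: 2.6% and 5.0% of the SD (n = 6000); 3.6% and 7.2% of the SD (n = 3000).

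**Formulas**

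- Mean, in SD units: half-width = z/√n; full width = 2z/√n.
- Proportion at p = 0.5: half-width = z × √(0.25/n); full width = twice that.

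**Reproducing the other three figures**

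- Proportion, n = 6000: 1.95996 × √(0.25/6000) = 1.265%; full width 2.530%. The stated 2.6% holds.
- Proportion, n = 3000: 1.95996 × √(0.25/3000) = 1.789%; full width 3.578%. The stated 3.6% holds.
- Mean, n = 3000: 1.95996/√3000 = 0.03578 SD; full width 7.157% of the SD. The stated 7.2% holds.

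These are evidently the formulas the protocol used.

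**The figure in question: mean, n = 6000**

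- Half-width: 1.95996/√6000 = 1.95996/77.460 = 0.02530 SD. To three decimals this is the stated 0.025.
- Full width: 2 × 0.02530 = 5.061% of the SD. The stated limit of 5.0% does not hold.
- With z rounded to 1.96 the width is 5.061%; with the t quantile on 5999 degrees of freedom it is 5.062%. Neither variant reaches 5.0%, and to one decimal all three give 5.1%.

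**Where the 5.0% probably comes from**

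Rounding each half-width to the digits printed and then doubling gives all four stated limits:

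| Parameter | n | Exact half-width | Rounded | Doubled | Exact full width |
|---|---|---|---|---|---|
| Proportion | 6000 | 1.265% | 1.3% | 2.6% | 2.530% |
| Mean | 6000 | 0.02530 SD | 0.025 SD | 5.0% of SD | 5.061% of SD |
| Proportion | 3000 | 1.789% | 1.8% | 3.6% | 3.578% |
| Mean | 3000 | 0.03578 SD | 0.036 SD | 7.2% of SD | 7.157% of SD |

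In three rows the rounding happens to go upwards, so the doubled figure is a valid limit. In the second row it goes downwards, and it is not. This also explains the broken factor of two: the exact n = 6000 widths, 2.530% and 5.061%, do stand in that relation.

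**Size of the discrepancy**

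- Absolute: 5.061% − 5.0% = 0.061 percentage points of an SD.
- Relative to the stated limit: 0.061/5.0 = 1.2%.
- In the units of the protocol's own example, age: the protocol gives no SD. If it is assumed to lie between 10 and 14 years, the excess width is 0.00061 × 10 = 0.006 years to 0.00061 × 14 = 0.009 years, or about 2 to 3 days.

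**The case against.** The best defence is that this is a rounding residue. The printed half-width of 0.025 SD is correct to the digits shown, one uniform convention explains all four figures, and no decision rule or success criterion uses the 5.0%. All of that stands, and it is why the point is minor. It does not rescue the sentence as worded. Rounding to the nearest digit suits an estimate, but a statement that a width will not be exceeded fails when the rounding lands below the true value.

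Three stronger readings are tempting, and the document does not support them.

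- **That the study is too small.** An interval of exactly ± 0.025 SD would need (1.96/0.025)² = 6146.6, that is 6147 patients per group, 147 more than planned. A reader might call this a shortfall. However, Sections 7.2.1 and 7.5 give 6000 per group as settled, and Section 7.5 then reports the precision that follows. The 5.0% was never a target from which the size was derived, so there is no requirement to fall short of.
- **That this figure breaks a deliberate round-up rule.** The other three limits do lie above their exact values, but ordinary rounding followed by doubling produces them. Nothing in Section 7.5 shows a separate convention.
- **That missing data make the error worse.** Incomplete values would widen the interval, but they would do so for every precision figure that rests on n. Sections 7.4 and 7.9 already acknowledge that routine data may be incomplete. This is a reason to state the basis of the figures, not further evidence of this slip.

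**Conclusion.** The limit of 5.0% of the SD for means with 6000 patients per group is wrong as written. The width is 5.06% of the SD (± 0.0253 SD). It is the only one of the four precision statements in Section 7.5 that fails.

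The result rests on the usual large-sample interval for a mean, with 6000 independent patients who all have a value for the parameter. It needs no figure from outside the protocol and does not depend on the choice between z and t.

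The point is a small correction of a stated precision. It changes no planned analysis and no interpretation, and it gives no ground for questioning the planned enrolment.

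**What to change.** Correct the one statement in Section 7.5, in either of two ways:

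- keep it as an upper limit, replacing 5.0% by 5.1% of the SD and ± 0.025 SD by ± 0.0255 SD (2 × 0.0255 = 0.051, so the two numbers agree, and both lie above the exact values of 5.061% and 0.0253); or
- give it as a value, approximately 5.06% of the SD (± 0.0253 SD).

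In either case, say that the figure applies to 6000 evaluable patients. The other three limits can stay as they are.

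The cost is an edit to one sentence and a marginally less favourable stated precision. Enrolment, data collection and analysis are unaffected.

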7.6 Data management

The designated CRO will supply the study site with access to an online eCRF that has been fully validated. Novartis or designated CRO will train designated study site staff on the eCRF system. Alternatively, self-administered online trainings may be applied. Study site staff will not be given access to the eCRF until they have been trained. Designated investigator staff will enter the data required by the protocol into the eCRF using a computer at site. The treating physician must approve that the data are complete and accurate and that all AEs were documented by signing the eCRF. Novartis or the designated CRO can raise manual queries in order to resolve discrepancies resulting from clinical/medical data review.

Concomitant medications entered into the database will be coded using the WHO Drug Reference List, which employs the Anatomical Therapeutic Chemical classification system. Medical history/current medical conditions and AEs will be coded using the Medical dictionary for regulatory activities (MedDRA) terminology.

At the end of data collection, data entry should be completed by the site and responses to open queries through the site staff should be shared, and data should be signed by a treating site physician. After these actions have been completed, the database will be locked for data analysis. Local laws, regulations and data privacy policies apply.

Data management will be performed by the designated CRO. All data management procedures will be performed in accordance with CRO's standard operating procedures (SOP) and will be described in detail in the project-specific data management plan (DMP).

Statistical analysis is performed using Statistical Analysis System (SAS®, Version 9.2 or higher).

7.7 Data analysis

All analyses will be performed by the designated CRO.

Only descriptive data analyses will be carried out, supported by calculation of confidence intervals. No statistical testing will be performed.

The two patient populations will be considered and analyzed separately. The SoC group will allow the representative picture of current CHF management as mentioned above. The Sacubitril/valsartan stratum will provide early insight into the adoption of this new therapy, once it will be available in the different countries. Therefore also strata for patients switching between SoC and Sacubitril valsartan will be analyzed upon adequate subgrouping.

The two studied groups, SoC and sacubitril/valsartan, are expected to differ significantly depending on the progressive adoption of sacubitril/valsartan by the prescribers – this will be assessed by stratified analysis according to the above described enrollment phases. In addition, besides baseline characteristics of the patients leading to the physicians' decision to prescribe sacubitril/valsartan or continue SoC, no inferences can be made from the comparison of the characteristics of both populations. For the same reason, no comparison of data obtained during the follow-up phase between the treatment groups is planned. Similarly, no safety comparisons will be performed between SoC (where in most cases an established therapy is merely continued) and sacubitril/valsartan (where a new therapy is prescribed).

Analyses will be performed for the total sample and stratified by demographic, anamnestic and medical factors (e.g. sex, duration of HF, severity of HF, previous HF-treatment) using an adequate grouping. Similarly, data will be also analyzed stratified according to enrollment phase (phase 1 and phase 3) and treatment group (e.g. SoC, valsartan/sacubitril, switching between both groups).

The Statistical Analysis Plan will be created as a separate document prior to data base lock for any analysis (e.g. interim analyses, final analysis). This document will contain sufficient details to enable the generation of the analysis of the NIS and specifies:

- the statistical database underlying the evaluation, including all adjustments, implementations and the calculation of derived variables,
- the detailed establishment of the analyzed population(s), and
- the statistical procedures.

